5.2.2 INCLUSION CRITERIA

All of the following inclusion criteria must be present for the patient to be enrolled in the trial.

- 1- Patient must be scheduled for percutaneous angiography, defined as diagnostic cardiac catheterization, or lower extremity or aortic iodinated contrast angiography.
- 2- Patients must have a Mehran score of at least 6 before the procedure.
- 3- Patients must have baseline creatinine and hemoglobin drawn before the procedure.
- 4- Signed informed consent.

5.2.3 EXCLUSION CRITERIA

None of the following exclusion criteria must be present for the patient to be enrolled in the trial

- 1- Patients on renal replacement therapy before randomization, will be excluded.
- 2- Being exposed to any types of nitrates 48 hours prior to randomization,
- 3- History of allergic reaction to any of the components of intravenous nitroglycerin.
- 4- Exposure to contrast media 4 days prior randomization.
- 5- Planned revascularization in the next 24 to 48 hours of the first PCI procedure.
- 6- The patient is hypotensive (<90/60mmHg) at the time of randomization.
- 7- Patients exposed to phosphodiesterase inhibitors 48 hours prior to randomization

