4.1 PRIMARY ENDPOINT

The primary endpoint for this trial will be to determine the change in glomerular filtration rate after exposure to contrast media. We will compare the change in GFR before and after percutaneous angiography of the group that received intravenous nitroglycerin with the change in GFR before and after percutaneous angiography of the group that did not receive intravenous nitroglycerin.

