4.2 SECONDARY ENDPOINTS

Major secondary endpoints will include:

[figure not shown]
- 1- Incidence of CIN, defined as an increase in baseline serum creatinine of 25% or ≥ 0.5 mg/dl 48 to 72 hours post-percutaneous angiography
- 2- Safety profile of the interventions including volume overload, hypotension, headache, medication interaction, the need for hemodialysis, intra-aortic balloon pump, endotracheal intubation or the use of vasopressors.
- 3- Analysis and comparison to a CIN predictive score calculator (Mehran Score).

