5.3 STUDY ALGORythM

To achieve our primary and secondary end-points we will (1) screen patients in the catheterization lab and/or emergency department of Mount Sinai Medical Center. (2) After inclusion and exclusion criteria's are verified, informed consent will be signed by the patient. (3) a case report form will be completed. (4) The research staff will order a treatment protocol to be administered. (5) Laboratory studies will be performed if needed. (6) The patients will receive an intravenous infusion of nitroglycerin and/or saline for at least 1 hour. (7) Coronary angiography will be performed and another screening for exclusion criteria will be done by the coordinator and assistant investigators. (8) Variables such as volume of contrast and number of vessels stented will be obtained. (9) Patients will go to recovery area and another infusion will be started for another 3 hours. (10) 48 hours later patient will be contacted to come to the hospital for another set of laboratory studies or patients that stayed in the hospital will be contacted and all the information needed will be completed.

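### The repeat-procedure exclusion stops at 48 hours and names only planned revascularization after a PCI, so a planned second contrast load can precede the outcome creatinine

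*Combined protocol and SAP*

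**What the plan says.** Two exclusion criteria in section 5.2.3 bear on contrast exposure other than the index procedure. Criterion 4 looks backward: "Exposure to contrast media 4 days prior randomization". Criterion 5 looks forward: "Planned revascularization in the next 24 to 48 hours of the first PCI procedure". No other criterion concerns procedures after the index angiography.

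The index procedure, in section 5.2.2, is percutaneous angiography, "defined as diagnostic cardiac catheterization, or lower extremity or aortic iodinated contrast angiography".

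On outcome timing, section 4.2 defines CIN by a creatinine rise measured "48 to 72 hours post-percutaneous angiography". Section 5.3 says that "48 hours later patient will be contacted to come to the hospital for another set of laboratory studies", or that the information is completed in hospital for those who stayed; it gives no latest time for the draw. The primary endpoint carries no time in section 1.0 or section 4.1, which says only: "The primary endpoint for this trial will be to determine the change in glomerular filtration rate after exposure to contrast media".

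Section 5.3 repeats the screening for exclusion criteria around the procedure. Section 5.2.4 lists amount and type of contrast among the variables to be collected, but not contrast given between the index procedure and the outcome sample.

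**The concern.** The outcome creatinine should reflect one contrast exposure, the one that the randomised infusion surrounds. The infusion ends about 3 hours after the index procedure. A second contrast load before the sample adds a renal insult that this infusion was not given to prevent, and the resulting creatinine mixes the two.

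The forward exclusion ends where the CIN window opens. It is also limited in kind, because it names revascularization and counts from a PCI, while the admitted index procedures include purely diagnostic and peripheral angiography. A further diagnostic contrast study is not revascularization, and a patient with a diagnostic index procedure has, on the words used, no PCI to count from.

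Events that treatment does not influence, if equally frequent by arm, pull the relative risk towards 1 and add variance to the eGFR change. If re-exposure differed by arm, it would bias the comparison. The plan does not say how such patients are recorded or analysed.

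**Working it through.** **Step 1: the windows side by side, in hours after the index procedure**

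| Item | Section | Covers |
|---|---|---|
| Exclusion of a later procedure | 5.2.3, criterion 5 | up to 48 h (most generous reading); planned revascularization after a PCI |
| CIN creatinine | 4.2 | 48 to 72 h |
| Call for laboratory studies | 5.3 | from 48 h, no upper limit |
| Primary eGFR change | 1.0, 4.1 | not stated |
| Index procedure | 5.2.2 | diagnostic cardiac, lower-extremity or aortic angiography |

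For a CIN sample at 72 h, the uncovered interval is 72 − 48 = 24 h. For a sample at exactly 48 h it is 0 h for planned revascularization after a PCI, but other planned contrast procedures remain uncovered. For the primary endpoint the interval cannot be computed, because no sampling time is given. The repeat screening in section 5.3 uses the same list of criteria and so does not close the gap.

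**Step 2: reproduce the plan's sample size**

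Inputs from section 5.1: control rate p1 = 0.30, relative risk 0.5 (so p2 = 0.15), power 0.90, alpha 0.05, allocation 1:1. Sidedness is not stated; two-sided is used.

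n = [1.960 × √(2p̄(1−p̄)) + 1.282 × √(p1(1−p1) + p2(1−p2))]² / (p1−p2)², with p̄ = 0.225.

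n = 3.6175 / 0.0225 = 160.8, rounded up to **161 per arm**. This matches the plan. Power at 161 per arm is 0.900. At 200 per arm (the 400 patients of section 4.3, before any dropout) it is 0.951.

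**Step 3: illustrate the dilution**

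The documents give no frequency of second procedures. Assume that second loads cause CIN in a share s of patients who would otherwise be event-free, with the same s in both arms:

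- p1′ = 0.30 + 0.70s
- p2′ = 0.15 + 0.85s
- power = Φ{[(p1′−p2′) − 1.960 × √(2p̄′(1−p̄′)/n)] / √[(p1′(1−p1′) + p2′(1−p2′))/n]}

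| s (assumed) | p1′ | p2′ | RR | Power, 161 per arm | Power, 200 per arm |
|---|---|---|---|---|---|
| 0 | 0.300 | 0.150 | 0.50 | 0.900 | 0.951 |
| 2% | 0.314 | 0.167 | 0.53 | 0.873 | 0.933 |
| 5% | 0.335 | 0.1925 | 0.57 | 0.830 | 0.902 |

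**Step 4: what s implies**

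The quantity s is excess CIN, not the re-exposure rate. If a second load carries an added CIN risk a, the share re-exposed is s/a. Taking a = 0.14 or 0.30 (assumptions), s = 2% needs 0.02/0.14 = 14% or 0.02/0.30 = 7% re-exposed. For s = 5% the shares are 0.05/0.14 = 36% and 0.05/0.30 = 17%. The 5% row is therefore a demanding case.

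**The case against.** The strongest reply is that the gap is narrow.

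- **The first 24 hours.** A reader might infer that criterion 5 opens only at hour 24, leaving the first day uncovered. In ordinary usage the phrase means within the next day or two, and a rule that barred day 2 but allowed day 1 would be implausible. The text does not support that stronger claim.
- **Loose use of PCI.** Sections 2.3 and 5.3 use PCI and stenting language for the index procedure, so the first PCI may simply mean the index procedure. That is a fair reading, but it makes the criterion ambiguous rather than complete. A planned contrast study that is not revascularization still falls outside it.
- **The 4-day criterion.** A reader might take criterion 4 as the protocol's admission that contrast within 4 days disturbs renal function. The protocol gives no reason for it, and a backward washout for a clean baseline need not equal a forward window. The point does not depend on it.
- **Which endpoint.** The 48 to 72 hour window is stated only for the secondary CIN endpoint. For the primary eGFR change the defect is the missing time point, which leaves the exposure undefined. The dilution figures concern the CIN comparison; the added variance in eGFR change is not quantified.
- **Size.** At the planned 200 per arm, power stays at or above 0.90 in both illustrations. This stands.

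What remains is that, on every reading, some planned contrast before a permitted outcome sample is not excluded, and no rule governs unplanned contrast.

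**Conclusion.** The point holds in limited form. Sections 4.2, 5.2.2, 5.2.3 and 5.3 do not align. Planned contrast after 48 hours but before the sample, or planned contrast that is not revascularization after a PCI, is not excluded and would contaminate the outcome.

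The size cannot be derived from the documents. Under the assumed 2% to 5% excess CIN, equal by arm, the consequence is a modest dilution, and the margin between 161 and 200 per arm absorbs it before any dropout. A reader might infer that the trial is underpowered or the sample size miscalculated; neither follows, since 161 reproduces. Nor do the documents show that re-exposure would differ by arm, so a directional bias is not demonstrated.

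The change is worth making because it is cheap and because the outcome otherwise lacks a clean definition.

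**What to change.** 1. Reconcile sections 4.2, 5.2.2, 5.2.3 and 5.3. Reword criterion 5 to cover any planned repeat iodinated contrast, cardiac or peripheral, between the index angiography and the outcome creatinine.
2. State one sampling window, with an upper limit, for both the eGFR change and CIN.
3. Record any unplanned contrast given before the outcome sample. Keep these patients in the main analysis with their scheduled 48 to 72 hour value.
4. Pre-specify a sensitivity analysis that omits them, or that uses the last creatinine before re-exposure where one exists. An early pre-contrast value should not replace the outcome in the main analysis: it departs from the CIN definition and could miss CIN that has not yet appeared.

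Cost: revised wording, one added case report form field and one sensitivity analysis. A few patients with a staged procedure already planned would not be enrolled.

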1.0 EXECUTIVE SUMMARY

Study Design

This is a placebo controlled study in 400 patients, testing the hypothesis that pre-treatment use of intravenous nitroglycerin will decrease the incidence of renal insufficiency after percutaneous angiography, cardiac or lower extremity

Intervention

Patients undergoing percutaneous angiography will be randomly assigned to receive intravenous nitroglycerin (5 mcg/min, titrated up to 50mcg/min for at least 1 hour, maintaining systolic blood pressure (BP) > 100 mmHg, before and 3 hours after the procedure) or a normal saline placebo in a 1:1 ratio.

Enrollment period

The patients will be enrolled during a 2 year period.

Rationale for this study

Animal models suggest that the impaired synthesis of nitric oxide is one important contributor to the pathogenesis of the vasoconstriction caused by exposure to contrast-media. Our previous, retrospective, pilot study supported the hypothesis that the administration of nitrates, particularly intravenous nitroglycerin, before PCI, may decrease the incidence of contrast induced nephropathy (CIN).

Primary Endpoint:

- 1- The primary endpoint will be the change in estimated glomerular filtration rate (eGFR) assessed by modification of diet for renal disease formula, after percutaneous angiography.

Secondary Endpoints:

- 1- CIN will be defined as an increase in serum creatinine of 25% or ≥ 0.5 mg/dl post-percutaneous angiography.
- 2- Safety profile of the intervention including volume overload, hypotension, headache, the need for hemodialysis, intra-aortic balloon pump, endotracheal intubation or the use of pressors.
- 3- Analysis and comparison to a CIN predictive score calculator (Mehran Score).

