5.0 RESEARCH DESIGN AND METHODS

5.1 SAMPLE SIZE

NOT A CASE CONTROL STUDY. This is a randomized, placebo-controlled clinical trial with a 1:1 randomization of active therapy to placebo. Prior data from our retrospective study indicate that the failure rate among controls is 0.3. If the true relative risk of failure for experimental subjects relative to controls is 0.5, we will need to study 161 experimental subjects and 161 control subjects to be able to reject the null hypothesis that this relative risk equals 1 with probability (power) 0.9. The Type I error probability associated with this test of this null hypothesis is 0.05.

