5.2 STUDY POPULATION

5.2.1 PATIENT RECRUITMENT

The recruitment strategies for CoNaN trial are targeted to specific groups in order to meet study goals with respect to patient enrollment and demographics. Meeting these goals, which results in a study population that reflects the typical patient population with the disease/health characteristics of interest, is necessary for making informed conclusions based on data collected during the study.

CoNaN trial will randomize 400 patients with a Mehran score ≥ 6 in a 1 x 1 trial of intravenous nitroglycerin versus intravenous saline only. All patients must complete informed consent process prior to being randomized into the trial.

Patients will be recruited primarily from 2 different sites. (1) Mount Sinai Emergency department, once they are evaluated by cardiology and scheduled for a non-emergent catheterization. (2) Directly from the Mount Sinai Medical Center catheterization Laboratory.

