5.4 TREATMENT REGIMENS

Continuous intravenous infusion of nitroglycerin 5 mcg/min will be started and titrated every 3-5 minutes for a maximum of 100 mcg/minute if tolerated by blood pressure (>100/60mmHg), at least 1 hour before and 3 hours after the procedure. The nitroglycerin for infusion comes in a pre-mixed 250 ml bottle, with a concentration of 200 mcg/ml.

Intravenous sodium chloride 0.9%, will be administered at 1ml/kg/hr at least 1 hours before the procedure and at least 3 hours after for both treatment arms. If the ejection fraction is known to be less than 40% or patient have signs and symptoms of volume overload, a 0.5 ml/kg/hr regimen will be utilized. If the patient is in acute congestive heart failure, no intravenous fluids will be given.

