5.4.1.2 SEVERE HYPOTENSION

The most common adverse effect of Nitroglycerin is hypotension. Nitroglycerin forms free radical nitric oxide. In smooth muscle, nitric oxide activates guanylate cyclase which increases guanosine 3'5' monophosphate (cGMP) leading to dephosphorylation of myosin light chains and smooth muscle relaxation. This produces a vasodilator effect on the peripheral veins and arteries with more prominent effects on the veins, decrease preload (left ventricular end-diastolic pressure); may modestly reduce afterload. This can lead to severe hypotension and paradoxical bradycardia and increased angina pectoris can accompany hypotension.

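### The entry criteria admit patients with systolic BP of 90 to 100 mmHg, whom the trial's own nitroglycerin rules do not allow to be dosed as planned

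*Combined protocol and SAP*

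**What the plan says.** **Entry.** Section 5.2.3, exclusion 6, removes a patient if "The patient is hypotensive (<90/60mmHg) at the time of randomization". The inclusion criteria in section 5.2.2 set no minimum blood pressure.

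**Dosing.** Section 5.4 states "Continuous intravenous infusion of nitroglycerin 5 mcg/min will be started and titrated every 3-5 minutes". Its upper rate and the pressure condition attached to it read "for a maximum of 100 mcg/minute if tolerated by blood pressure (>100/60mmHg"). The planned duration is a minimum of 1 hour pre-procedure and 3 hours post-procedure. The executive summary (section 1.0, Intervention) gives a ceiling of 50 mcg/min instead and adds the condition "maintaining systolic blood pressure (BP) > 100 mmHg". The saline regimen in section 5.4 carries no blood pressure condition.

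**Later check.** Step 7 of the algorithm in section 5.3 screens again for the exclusion criteria at angiography. This follows the infusion of at least 1 hour in step 6, and no different pressure limit is given.

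**Safety context.** Section 5.4.1.2 says "The most common adverse effect of Nitroglycerin is hypotension". Section 4.2 lists as a secondary endpoint "Safety profile of the interventions including volume overload, hypotension, headache", among other events.

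**The concern.** The systolic floor for entry is 10 mmHg below the systolic floor for treatment, and nothing in the plan says how to dose a patient who falls between them. Staff could reasonably treat the same patient in two ways:

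- **Start and hold.** If the pressure condition in section 5.4 limits only up-titration, the patient starts at 5 mcg/min and stays there until pressure rises. No limit in section 5.4 is breached, but little drug is given before contrast. The trial's hypothesis concerns pre-treatment, so that hour matters most.
- **Do not run.** If the executive summary's condition applies from the start, a patient at 95 mmHg does not meet it even at the lowest rate. Infusing then means giving a vasodilator below the trial's own floor.

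Either way the problem falls on the nitroglycerin arm alone. The stakes are a weaker treatment contrast on the first reading and avoidable hypotension risk on the second.

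**Working it through.** **1. Thresholds side by side (systolic BP)**

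| Rule | Section | Patient at 95/65 mmHg |
|---|---|---|
| Excluded if below 90/60 | 5.2.3 | Eligible |
| Minimum BP for inclusion: none | 5.2.2 | Eligible |
| Keep systolic above 100 | 1.0 | Not met |
| Titrate if above 100/60 | 5.4 | Not met |
| Re-screen on the exclusion criteria | 5.3, step 7 | Still passes, and comes after the first hour of drug |

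The affected band is systolic 90 to 100, with 100 included because the dosing rules require more than 100. The diastolic figure is 60 in both 5.2.3 and 5.4, so the conflict is in systolic pressure.

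**2. Dose under start-and-hold**

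Dose = rate × minutes, with 60 min before contrast and 240 min in total (1 h before plus 3 h after).

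| Rate held throughout | First 60 min | 240 min |
|---|---|---|
| 5 mcg/min (start rate) | 300 mcg = 0.3 mg | 1,200 mcg = 1.2 mg |
| 50 mcg/min (ceiling, 1.0) | 3,000 mcg = 3 mg | 12,000 mcg = 12 mg |
| 100 mcg/min (ceiling, 5.4) | 6,000 mcg = 6 mg | 24,000 mcg = 24 mg |

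A held patient gets 10% or 5% of the ceiling dose. The ceiling rows are upper bounds, because a titrated patient does not start at the ceiling.

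**3. The plan's own sample size**

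Section 5.1 says "the failure rate among controls is 0.3" and takes a relative risk of 0.5, so the active rate is 0.15. It states power 0.9 and alpha 0.05. Sidedness is not stated; two-sided is used here because it reproduces the plan's figure. With p̄ = (0.30 + 0.15)/2 = 0.225:

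- s0 = √(2 × 0.225 × 0.775) = 0.5906
- s1 = √(0.30 × 0.70 + 0.15 × 0.85) = 0.5809
- n = [(1.960 × 0.5906 + 1.2816 × 0.5809)/0.15]² = 160.8, so 161 per arm, as the plan states.

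Power at n per arm is Φ[(d√n − 1.960 × s0)/s1], where d is the difference in rates. It is 0.900 at n = 161 and 0.951 at n = 200, the planned 400 patients split 1:1.

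**4. Illustrative dilution of the CIN comparison**

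Let f be the share of the active arm in the band and b the share of benefit they keep. The documents give neither, so both are assumed. Active rate = 0.15 + 0.15 × f × (1 − b). Extra expected CIN cases = 200 × f × 0.15 × (1 − b).

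| f | b | Active rate | Patients affected | Extra cases | Power, n = 200 per arm |
|---|---|---|---|---|---|
| 0 | – | 0.1500 | 0 | 0 | 0.951 |
| 0.01 | 0 | 0.1515 | 2 | 0.3 | 0.947 |
| 0.05 | 0 | 0.1575 | 10 | 1.5 | 0.927 |
| 0.10 | 0 | 0.1650 | 20 | 3.0 | 0.895 |
| 0.05 | 0.5 | 0.15375 | 10 | 0.75 | 0.940 |
| 0.10 | 0.5 | 0.1575 | 20 | 1.5 | 0.927 |

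Power falls to 0.90 at f = 0.093 when b = 0, and at about f = 0.185 when b = 0.5.

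**5. Primary endpoint**

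The plan gives no standard deviation or target difference for the change in eGFR, so the same calculation cannot be done for it.

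**The case against.** The strongest reply is that an entry limit and a titration limit serve different purposes and need not match. Section 5.4 says the drug is started and then titrated as pressure allows. A patient at 95/65 starts at 5 mcg/min and goes up if pressure permits, and the executive summary's wording can be read the same way. **This stands in part.** On that reading nothing in section 5.4 is breached. But the plan never says which reading applies, and start-and-hold still leaves the patient on the minimum rate before contrast.

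Second, the dose comparison sets a patient whose pressure never rises against one at the ceiling from the first minute. **This stands.** The figures bound the gap and do not describe a typical pair. A patient entering at 102 mmHg might stall at almost the same dose.

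Third, few patients may be affected. Emergency-department recruits are described as "scheduled for a non-emergent catheterization", no passage says 5 mcg/min is ineffective, and randomisation balances low-pressure patients in expectation, so the efficacy effect is dilution and not bias. **This stands** and is why the point is minor. On the other side, the Mehran score used for entry gives points for heart failure and low ejection fraction, so selection does not obviously steer away from low pressures.

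Fourth, a dosing rule alone would be lighter than a new exclusion, since any treated patient's pressure may fall and the plan aims for a typical population. **This stands in part.** The dosing rule is needed in any case. Without the entry change, though, the trial would still randomise patients whom its own systolic floor bars from the planned dose.

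**Conclusion.** The mismatch is established by the text alone. A patient with systolic BP of 90 to 100 mmHg can be randomised, yet the stated rules lead either to a near-minimal dose before contrast or to nitroglycerin infused below the trial's own floor. No other section resolves it.

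Its size is minor. The documents give no blood pressure distribution, so the affected share is unknown. The power figures concern CIN, a secondary endpoint. They rest on the plan's rates, 200 per arm and an assumed loss of benefit. They do not show an underpowered trial: with no benefit kept, power is below the planned 0.90 only if more than about 9% of the arm is affected. Confidence is high for the threshold conflict; its practical effect remains unquantified.

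**What to change.** 1. **Section 5.2.3, exclusion 6:** exclude systolic BP of 100 mmHg or less at randomisation, subject to clinical confirmation of the value, and check it before the coordinator completes the randomisation screen (section 5.2.5). No separate exclusion for diastolic BP of 60 or less is needed.
2. **Section 5.4:** add one sentence saying whether to hold, reduce or stop nitroglycerin when systolic BP falls to 100 or below during infusion. Some under-dosing from falls during titration will remain after the entry change, so this is needed as well.
3. **If enrolment has begun:** count the randomised patients in the 90 to 100 band from the blood pressure listed in section 5.2.4. That section does not say when the reading is taken, so confirm that it reflects the time of randomisation.

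The cost is a one-line amendment and one added sentence, with no new data collection. Some low-pressure candidates become ineligible. The effect on accrual cannot be estimated from the documents.
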